Study Title: Whey Protein Support to Metabolic and Performance Adaptations in Response to High Intensity Interval Training in Young Adult Men

NCT: 7867835

Date: 14th May 2018

Detailed study protocol 7867835

Baseline screening

Prior to experimental testing, participants will attend the lab to complete baseline screening including an incremental cycle ergometer test to exhaustion to determine maximal oxygen update (VO₂max) via indirect calorimetry. A body composition assessment via bioelectrical impedance analysis (BIA) will also characterise participants for inclusion in the study (BMI <30 kg.m⁻²). The protocol to determine VO₂max comprises a 5 minute warm-up stage at 50 W with subsequent 1 minute incremental stages (30 W) until exhaustion. The following criteria are used to establish if VO₂max has been achieved: Volitional fatigue, Rate of perceived exertion (RPE) \geq 18, respiratory exchange ratio (RER) \geq 1.10, and heart rate (HR) \geq 85% age-predicted max.

Pre-intervention performance testing

Following baseline screening, included participants attend the lab 2 h after a standardised meal and having refrained from caffeine on the day of testing, to complete pre-intervention performance testing. This comprises in order a baseline i) Wingate test; ii) Submaximal incremental cycling test; iii) 20 minute cycling performance test.

Wingate Test

After recording height and weight, participants complete a standardised 5 minute warm-up on a Wingate cycle ergometer, followed by 30 s maximal cycle sprinting against a resistance equivalent to 7.5% of their body mass (BM). A 3 minute cool down period follows this test.

Submaximal incremental cycling test

After 15 minutes seated rest, participants begin a submaximal incremental cycle test consisting of a 2 minute standardised warm-up followed by 4 minute stages starting at 50 W and incrementing by 50 W after each completed stage. The test ends after the final stage is completed, corresponding to a power output of 250 W, or when participants can no longer maintain a cadence of \geq 80 rpm during exercise. Participants must also maintain their cadence within a range of 80-85 rpm throughout the test. RPE and HR are used as markers of exercise intensity during this test. Capillary lactate is sampled at rest and during the final 30s of each stage and concentrations are determined using a handheld meter. Power output at the lactate threshold (W_{LT}) is calculated from this data. Cycling economy (CE) is calculated by determining the ratio of oxygen uptake to power output during the last 30s of each stage.

20 minute cycling performance test

After 15 minutes of seated rest, participants complete a 20 minute cycling performance test where they are instructed to exert maximal effort throughout the 20 minute period. RPE and HR are monitored at 5 minute intervals throughout the test. Mean power output and total work are calculated and used as performance markers for this test.

Dietary controls

A 7 day weighed food diary is administered before the beginning of the HIIT intervention in order to characterise habitual dietary intake and analyse each participant's energy and macronutrient intake. Participants are instructed to maintain their habitual dietary intake throughout the HIIT intervention. A 24 h dietary recall is conducted upon each visit to the lab for participants, and dietary analysis using this information is compared with the 7 day food diary analysis to assess maintenance of habitual dietary intake for the duration of the HIIT intervention.

Nutritional intervention

All 3 supplement/placebo drinks are matched for volume, flavour (Synergy[®] Flavours, Carbery Food Ingredients Ltd) and appearance while the whey protein concentrate (WPC) and whey protein hydrolysate (WPH) drinks are matched for protein content. For each exercise session, participants attend the lab the morning after a ≥10 h overnight fast, and ingest 0.33g.kg⁻¹ BM protein of WPC or WPH, or 0.33 g.kg⁻¹ BM of a flavoured placebo. All drinks are ingested 45 minutes pre-exercise, and are all food grade and safe for human consumption. Participants are also provided with a standardised post-exercise snack (2.43kcal.kg⁻¹ BM, 0.25g.kg⁻¹ BM protein) which they were instructed to consume 30 minutes after each exercise session (*excluding exercise session 1*).

Experimental design

This study will be conducted in a randomised, double-blind (participants and outcomes assessor blind) parallel groups design. Participants are randomly allocated into one of 3 nutritional intervention groups; fasted placebo, WPC fed or WPH fed. The exercise intervention comprises 9 HIIT sessions completed over 3 weeks with 48h rest in between exercise sessions. HIIT sessions will consist of 4-6 (4 sprints in the initial 3 sessions, 5 sprints in the middle 3 sessions, and 6 sprints in the final 3 sessions) X 30s maximal cycle sprints on a Wingate cycle ergometer, pedalling at a resistance equivalent to 7.5% BM. Each sprint is interspersed with 4 minutes active recovery. Standardised 5 minute warm-up and 3 minute cool-down periods precede and follow each exercise session, respectively. On the morning of each exercise session, participants arrive to the lab after a $\geq 10h$ overnight fast, having abstained from caffeine for 12h, alcohol intake for 24h and vigorous exercise 48h beforehand. On the morning of exercise session 1, a resting micro-needle muscle biopsy will be obtained under local anaesthetic (1% lidocaine) from m. vastus lateralis, as well as a venous blood sample. Following this, participants ingest the allocated pre-exercise drink and rest quietly in the lab for 45 minutes before beginning exercise. Further venous blood samples are obtained immediately pre and post-exercise. For exercise session 1, HIIT comprises 4 X 30s "all out" Wingate sprints, interspersed with 4 minutes active recovery. A fourth venous blood sample is obtained 1 h postexercise, as well as a second muscle biopsy, which is obtained 3 h post-exercise using the same procedures as before. Between the post-exercise recovery period and second muscle biopsy, participants are not permitted any food or drinks except for consuming water ad libitum. For the remaining exercise sessions, participants arrive the lab under the same conditions, ingest their allocated pre-exercise drink and rest quietly for 45 minutes before completing HIIT. They are also

provided with a standardised snack (2.43kcal.kg⁻¹ BM, 0.25g.kg⁻¹ BM protein) to consume 30 minutes following post-HIIT. Following HIIT session 9, a final muscle biopsy and venous blood sample are obtained 48-72h post-exercise under the same conditions (overnight fasted) and using the same procedures. Anaerobic exercise performance markers are obtained for each HIIT session (exercise sessions 1-9) as well as for individual sprints within-session (sprints 1-6) including peak power, mean power, total work and fatigue index.

Post-intervention performance testing

The performance testing completed pre-intervention (pre-intervention performance testing) is repeated by participants in an identical manner 72-96 h following completion of the final HIIT session. 24 h dietary recall is repeated for this lab visit, and participants refrain from caffeine intake and attend the lab 2 h following a standardised meal.

Statistical Analysis Plan

Normality and homogeneity of variance are tested prior to statistical tests. Paired sample t-tests will be used to assess within group changes. Between group treatment effects will be evaluated using a One-way ANOVA to examine the main effects of treatment based on delta scores from pre to post intervention. If the ANOVA yields a significant effect, post hoc comparisons will be performed using a bonferroni correction. A probability level P < 0.05 will be considered statistically significant and *cohen's d* effect sizes will be calculated. All normal data will be expressed as Mean ± Standard Deviation/Standard Error, or non-parametric as median (Interquartile Range).

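### Does the missing calculation rule for power at the lactate threshold (W_LT) need to be repaired in the plan?

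*Combined protocol and SAP*

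**What the plan says.** The section on the submaximal incremental cycling test sets 4-minute stages from 50 W in steps of 50 W. Capillary lactate is measured at rest and at the end of each stage with a handheld meter. On the endpoint it says "Power output at the lactate threshold (W_{LT}) is calculated from this data" and nothing more. On the upper limit it says "The test ends after the final stage is completed, corresponding to a power output of 250 W", with an earlier stop if cadence falls below 80 rpm.

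The order of testing is fixed in the section on pre-intervention performance testing: "This comprises in order a baseline i) Wingate test; ii) Submaximal incremental cycling test; iii) 20 minute cycling performance test". For the Wingate sprint, "A 3 minute cool down period follows this test". Fifteen minutes of seated rest and a 2-minute warm-up then precede the first lactate stage. The post-intervention section repeats the battery unchanged.

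Baseline screening says that the body-composition assessment "will also characterise participants for inclusion in the study", with BMI below 30. No fitness limit is given.

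The Statistical Analysis Plan compares arms by one-way ANOVA "based on delta scores from pre to post intervention". It adds "If the ANOVA yields a significant effect, post hoc comparisons will be performed using a bonferroni correction" and "A probability level P < 0.05 will be considered statistically significant". It names no primary outcome and does not mention undetermined values.

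**The concern.** A lactate threshold is derived from a curve, and the common derivations need not move by the same amount when the curve moves. If the rule is chosen after the data are seen, the comparison between arms can depend on that choice. The Bonferroni step does not cover this, because it applies only to comparisons between arms after a significant ANOVA.

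Two features of the test sharpen the worry. Lactate left over from the sprint may lift the whole curve, so a fixed concentration may already be exceeded at 50 W. The 250 W ceiling means that a man who improves past it loses his post-intervention value and so his change score. Missingness would then depend on the outcome.

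**Working it through.** The documents give no lactate value, W_LT, SD or sample size, so there is no planned figure to reproduce. Only the timing and the stage grid come from the protocol. All other inputs below are assumptions.

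**Timing.** The lactate test starts 3 + 15 = 18 min after the sprint. The first stage sample falls at 18 + 2 + 4 = 24 min, and later ones at 28, 32, 36 and 40 min.

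**Rules on a clean curve.** Assume 1.0, 1.3, 2.0, 3.8 and 8.0 mmol/L at 50 to 250 W, 0.95 at 0 W, a resting value of 1.0, and monotone cubic interpolation between points. Crossings are read by linear interpolation between stages. For example, the 4 mmol/L point is 200 + 50 × (4 − 3.8)/(8.0 − 3.8) = 202.4 W. Moving the curve right by 20 W gives:

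| Rule | Before (W) | After (W) | Change (W) |
|---|---|---|---|
| Fixed 4 mmol/L | 202.4 | 217.8 | 15.4 |
| Rest + 1 mmol/L | 150.0 | 164.0 | 14.0 |
| Lowest stage + 1 mmol/L | 150.0 | 162.8 | 12.8 |
| Cubic Dmax | 172.3 | 172.6 | 0.3 |

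The three crossing rules differ by 15.4 − 12.8 = 2.6 W. The near-zero comes from Dmax alone and needs both tests to run to 250 W. If the first test ends after 200 W and the second reaches 250 W, the Dmax change on the same curve is about +32 W.

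**Carry-over from the sprint.** Assume peak lactate P of 8, 10, 12 or 15 mmol/L and half-life h of 10, 15 or 20 min, which makes 12 scenarios. The excess at 18 min is (P − 1) × 0.5^(13/h), and it keeps decaying afterwards.

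- Mildest case, P = 8 and h = 10: 7 × 0.5^1.3 = 2.84, so the sample after the seated rest reads 1.0 + 2.84 = 3.8 mmol/L.
- Worst case, P = 15 and h = 20: 14 × 0.5^0.65 = 8.92, so that sample reads 9.9 mmol/L. The lowest stage value is at 150 W: 2.0 + 14 × 0.5^(27/20) = 7.5 mmol/L, so 4 mmol/L is never crossed.

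With the same carry-over at both visits and a 20 W shift:

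| Rule | Scenarios with a value | Change (W) |
|---|---|---|
| Fixed 4 mmol/L | 4 of 12 | 20-30 |
| Rest + 1 mmol/L | 9 of 12 | 17-26 |
| Lowest stage + 1 mmol/L | 12 of 12 | 13-26 |

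If clearance is 1.4 times faster once cycling starts, the counts are 6, 7 and 12. Some rules can therefore fail on these inputs. The resting and 50 W samples already planned would show it, at 3.8-9.9 and about 2.6-8.3 mmol/L against 1.0 when clean.

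**The 250 W ceiling.** Without carry-over and with a between-man SD of 20-40 W, the 4 mmol/L point lies above 250 W in 1-12% of men before and 12-26% after a mean 20 W shift. The mean true shift among men kept is 18.9-19.0 W, a bias of 20 − 19.0 = 1.0 to 20 − 18.9 = 1.1 W. For lowest stage + 1, the share above 250 W is at most 1.5%.

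**False positives.** The simulation used three arms of 8, 10 or 15 men, no arm effect and ANOVA on change. A single fixed rule gives about 5%. Reporting the smallest P of three rules gives 13-14% without carry-over and 9-11% with it.

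**Cost of the suggested rule.** With an assumed meter SD of 0.3 mmol/L and a clean curve, lowest stage + 1 has an SD of about 18 W per value, against about 4 W for 4 mmol/L. With independent errors the SD of a change is 18 × √2, about 25 W, against a response of 12.8 W. For 4 mmol/L it is 4 × √2, about 6 W, against 15.4 W. Under carry-over the SDs per value are 11-12 W for lowest stage + 1, 5-7 W for rest + 1, and 8-24 W for 4 mmol/L where it is determined. The ranking depends on how much carry-over there is, and the documents do not show that.

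**The case for a change.** The best case for a change is that nothing in either part of the document supplies a rule, that writing one costs no sample or visit, and that blinding does not settle the matter. The design section blinds participants and the outcomes assessor; it does not say that whoever chooses the rule is blind to allocation. A second calculation, with an exponential lactate curve and a different residue range, also found no Dmax response. In it the 4 mmol/L rule was undetermined in 9 of 16 carry-over scenarios.

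What stands is that the text is silent, and that a rule unable to cope with raised starting lactate would lose men from the change-score analysis. What does not stand is the step from there to an error in the plan. The 9-14% rate describes deliberate selection among rules, which the plan nowhere invites. Stable carry-over falls on both visits and largely cancels in the change. The ceiling biases the mean by about 1 W in the illustration. The resting sample is naturally read as the one taken after the seated rest. Stating that timing, reporting undetermined values by arm and visit, and labelling other rules as sensitivity analyses would record ordinary practice without altering a method.

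**Conclusion.** This is a gap that analysts can fill sensibly, and no change to the plan follows. The plan states no threshold rule that gives a wrong result. One sensible rule, applied alike to both visits and all arms, keeps the error rate near 5% and does not by itself favour an arm. The only concrete alternative replaces no stated method. It buys a value for every man at the price of a change-score SD of about 25 W against a 12.8 W response on the clean curve, and statisticians could reasonably disagree about that.

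The differences in watts, the counts of undetermined values and the error rates all rest on assumed curves, peaks, half-lives, meter noise and arm sizes. They show that the choice of rule can matter, not how much it matters in this trial. The point is confined to W_LT, one of many performance markers, with none labelled primary.

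### Maintenance of habitual diet is checked with 24 h recalls against a 7-day weighed diary, so a reporting difference between the instruments cannot be separated from a change in diet; add a recall-to-recall check by arm

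*Combined protocol and SAP*

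**What the plan says.** The Dietary controls section fixes the reference value first: "A 7 day weighed food diary is administered before the beginning of the HIIT intervention in order to characterise habitual dietary intake". The later measurement uses another method: "A 24 h dietary recall is conducted upon each visit to the lab for participants". The two are then set against each other: "dietary analysis using this information is compared with the 7 day food diary analysis to assess maintenance of habitual dietary intake". Under Post-intervention performance testing, "24 h dietary recall is repeated for this lab visit"; no second weighed diary is mentioned.

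No calibration between the two methods is described, nor any tolerance for calling diet maintained. The Statistical Analysis Plan section contains no dietary analysis. It has paired t-tests for changes within groups and a one-way ANOVA on pre-to-post changes for differences between groups.

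The Nutritional intervention section gives the amounts used below. Before each session participants "ingest 0.33g.kg⁻¹ BM protein of WPC or WPH, or 0.33 g.kg⁻¹ BM of a flavoured placebo". The post-exercise snack supplies 2.43 kcal/kg and 0.25 g/kg protein, and is given at all sessions "excluding exercise session 1".

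**The concern.** Every baseline value in this check comes from a prospective weighed record, and every later value comes from a retrospective recall. If the two methods report the same true intake differently on average, the whole of that difference lands on the before-versus-during comparison. An apparent rise or fall may then be only the change of method, and a real change of similar size in the opposite direction may be hidden.

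The plan appears to collect what is needed to avoid this. Recalls are due at every visit, so those at pre-intervention testing and on the morning of session 1 describe days before the first drink. The plan names only the diary as comparator.

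At stake is the claim that diet was stable, and with it how far the within-group changes can be read as responses to training and drink rather than to altered eating.

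**Working it through.** The plan states no figure on this point, so there is nothing to reproduce. The steps below put a scale on it.

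**Inputs from the documents (Nutritional intervention, Experimental design):** whey drink 0.33 g/kg protein; snack 2.43 kcal/kg and 0.25 g/kg protein; 9 sessions in 3 weeks; no snack at session 1, hence 9 drinks and 8 snacks in 21 days.

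**Assumptions, not in the documents:** 4 kcal per g protein, counting only the protein in the drink; body mass 80 kg; habitual intake 2,500 kcal/day; systematic instrument difference 5 to 15% of energy, sign unknown.

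**1. Energy of drink plus snack, whey arms**
- Drink: 0.33 × 4 × 80 = 105.6 kcal
- Snack: 2.43 × 80 = 194.4 kcal
- Session day: 105.6 + 194.4 = 300 kcal
- 21-day average: (9 × 105.6 + 8 × 194.4) / 21 = 2,505.6 / 21 ≈ 119 kcal/day
- Session day at 65 to 85 kg: 3.75 kcal/kg gives 244 to 319 kcal

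The placebo's energy content is not stated, so these figures cover the two whey arms only.

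**2. Assumed instrument difference**
- 5%, 10% and 15% of 2,500 = 125, 250 and 375 kcal/day
- Needed to equal the session-day total: 300 / 2,500 = 12% (15% at 2,000 and 10% at 3,000 kcal/day)
- Needed to equal the 21-day average: 119 / 2,500 = 4.8% (6.0% at 2,000 and 4.0% at 3,000 kcal/day)

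On energy, the assumed range covers the 21-day average almost throughout, and the session-day total only in its upper part.

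**3. The same question for protein**
- Session day: 0.33 + 0.25 = 0.58 g/kg. At an assumed habitual 1.0, 1.2, 1.5 or 1.8 g/kg/day, the instrument difference would have to be 58%, 48%, 39% or 32%.
- 21-day average: (9 × 0.33 + 8 × 0.25) / 21 = 0.237 g/kg/day, which needs 24% at 1.0 and 13% at 1.8 g/kg/day.

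The session-day protein is far outside 5 to 15%. The average touches that range only at the highest habitual intake. The comparison in size is therefore made for energy only.

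**4. Precision of a recall baseline**

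With within-person day-to-day coefficient of variation CV, the SD of (mean of later days minus mean of baseline days) is CV × √(1/baseline days + 1/later days). With 9 later recalls, and kcal at an assumed CV of 25% and 2,500 kcal/day:
- 7-day diary: √(1/7 + 1/9) = 0.504 CV, about 315 kcal
- three recall days: √(1/3 + 1/9) = 0.667 CV, about 417 kcal, 32% larger
- two recall days: √(1/2 + 1/9) = 0.782 CV, about 489 kcal, 55% larger

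Read as separate pairs, each baseline is a single day: session 1 against sessions 2 to 9 gives √(1 + 1/8) = 1.06 CV, and pre- against post-testing gives √(1 + 1) = 1.41 CV. This random error shrinks with the square root of the number of participants in an arm, which the documents do not state. A systematic instrument difference does not shrink.

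**The case against.** The strongest reply is that this hardly touches the trial's conclusions. Allocation is randomised, participants and outcomes assessor are blind, and the treatment effect is a between-group ANOVA on outcome changes that uses no dietary data. An offset common to all arms would also drop out of any comparison of dietary change between arms. This stands. A reader might infer that the drink effect itself is biased; that would require reporting to differ by arm, and the documents give no reason to expect it.

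A second reply is that size and direction are assumed. This also stands. It is tempting to say that recalls will read low and show a false fall in intake, or that the artefact is as large as the supplement under study. The documents support neither: they give no size or sign, and the equivalence fails for session-day protein.

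Third, drink and snack are prescribed additions, not lapses from habitual diet. If a recall covers the 24 h before a morning visit, 48 h between sessions means it would usually miss them. They serve here only as a yardstick.

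Fourth, swapping a 7-day baseline for two or three recall days costs precision, as shown. The pre-test recall would also include a standardised meal, and a third baseline day relies on a screening recall that the Baseline screening section does not mention. This argues against discarding the diary comparison, not against adding a like-for-like one. Because post-testing repeats the pre-test conditions, the meal is matched within that pair. Session 1 likewise shares its fasting, alcohol and exercise restrictions with later sessions.

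**Conclusion.** The concern holds in a limited form. Method and period are fully confounded in the only dietary check the plan describes, and nothing in the documents separates a reporting difference from a true change. Under the stated assumptions the artefact is 125 to 375 kcal/day in either direction, against about 300 kcal on a session day or about 119 kcal/day on average for drink plus snack, in energy and in the whey arms. The reach is narrow: the statement that habitual diet was maintained, and the interpretation of the paired within-group changes. The between-group test of treatment is not called into question. This is a minor point, worth acting on because the remedy is cheap.

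**What to change.** In Dietary controls and in the Statistical Analysis Plan, add a comparison of recalls with recalls, reported by arm, as the main check of maintenance:

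- session 1 morning recall (before the first drink) against recalls at later sessions;
- pre-intervention testing recall against post-intervention testing recall.

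State explicitly that a recall is taken at pre-intervention testing and at session 1, since this now follows only from the general wording about each visit. Keep the 7-day weighed diary to describe habitual intake, and report the recall-to-diary comparison alongside with a note that the methods differ.

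Cost: wording and a little analysis, with no new data if recalls are taken at every visit as planned. The downside is precision. The recall baseline rests on two or three days in all (one day within each pair), so it is noisier per participant than the diary. Results should be given as arm means with confidence intervals, not as verdicts on individuals.

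### The baseline and final resting biopsy and blood samples are matched on the fast but not on the previous day's food, which adds reducible noise to those deltas although the intake is already recorded

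*Combined protocol and SAP*

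**What the plan says.** **Baseline sample.** Under Experimental design: "On the morning of exercise session 1, a resting micro-needle muscle biopsy will be obtained under local anaesthetic", together with a venous blood sample. Participants arrive on every session morning after an overnight fast of at least 10 h, "having abstained from caffeine for 12h, alcohol intake for 24h and vigorous exercise 48h beforehand".

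**Final sample.** The end of the same section says that "a final muscle biopsy and venous blood sample are obtained 48-72h post-exercise under the same conditions (overnight fasted) and using the same procedures". The bracket names only the fast. Whether the caffeine, alcohol and exercise restrictions also carry over is left to the words before it.

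**Diet between visits.** Under Dietary controls: "Participants are instructed to maintain their habitual dietary intake throughout the HIIT intervention". Intake on the day before each visit is recorded: "A 24 h dietary recall is conducted upon each visit to the lab for participants". The one stated use of that record is that it "is compared with the 7 day food diary analysis to assess maintenance of habitual dietary intake for the duration of the HIIT intervention".

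**Performance tests.** These visits have a further control. Before the intervention, "included participants attend the lab 2 h after a standardised meal and having refrained from caffeine on the day of testing". Afterwards, "participants refrain from caffeine intake and attend the lab 2 h following a standardised meal".

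**Analysis.** The Statistical Analysis Plan uses paired t-tests for change within each group, and a one-way ANOVA on pre-to-post delta scores between the three groups. It names no covariate.

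**The concern.** Each baseline-to-final resting delta is the difference between one fasted sample before training and one after it. No repeat sample averages out day-to-day variation. Keeping to a habitual diet is a statement about the general pattern of eating. It does not make two particular days alike in energy, carbohydrate or protein. To the extent that a muscle or blood measure responds to the previous day's food, a difference between the two days enters the delta directly.

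Two things are at stake:

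- Differences that vary from man to man widen the spread of the deltas. This costs precision in both the paired t-tests and the ANOVA.
- A shift common to participants, such as generally eating more or less before the last visit than before the first, moves the mean delta in every arm. All arms train, so a paired t-test cannot separate such a shift from a response to training.

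The plan already collects the information needed to make the two days more alike, but does not use it for that purpose.

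**Working it through.** The plan gives no sample size, SD, effect size or power for any outcome, so there is no figure of its own to reproduce. The check has two parts.

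**1. What is matched between the two resting samples**

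| Condition | Session 1 (baseline) | Final visit |
|---|---|---|
| Overnight fast | at least 10 h | overnight fasted |
| Caffeine, alcohol, vigorous exercise | 12 h, 24 h, 48 h | implied by the reference to the same conditions, not restated |
| Food on the day before | habitual-intake instruction only | habitual-intake instruction only |
| 24 h recall taken | yes | yes |
| Recall used to match the days or adjust the delta | no | no |

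Suppose that day-before diet contributes variance v to the measure at each visit, and that its contributions at the two visits have correlation r. Its share of the delta variance is then v + v - 2rv = 2v(1 - r). The habitual-intake instruction may raise r; repeating the recorded day pushes r towards 1. The present control is therefore partial, and the remaining noise can be reduced.

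The acute session 1 changes (biopsies at rest and 3 h after exercise, bloods up to 1 h after) all follow the same previous day, so this component does not arise from a difference between two days.

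**2. What matching could be worth, under stated assumptions**

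Let f be the share of delta variance due to day-before diet, and q the fraction of that share removed by repeating the day. The remaining variance is (1 - fq) times the old. The variance of a group mean is proportional to variance/n, so the equivalent gain in participants is 1/(1 - fq) - 1. Neither f nor q is in the documents. I take f from 0 to 0.30 and q up to 1.

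- f = 0: 1/1 - 1 = 0%
- f = 0.10, q = 0.5: 1/0.95 - 1 = 5%
- f = 0.10, q = 1: 1/0.90 - 1 = 11%
- f = 0.30, q = 0.5: 1/0.85 - 1 = 18%
- f = 0.30, q = 1: 1/0.70 - 1 = 43%

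The same range can be expressed as power. The further assumptions are a total delta SD of 1, a true difference between two arms of 1, a two-sided alpha of 0.05, one pairwise comparison by the normal approximation, and q = 1. The SD after matching is sqrt(1 - f).

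| f | SD of delta | n per group for 80% power | Power at an assumed 10 per group |
|---|---|---|---|
| 0 | 1.000 | 16 | 0.61 |
| 0.05 | 0.975 | 15 | 0.63 |
| 0.10 | 0.949 | 15 | 0.65 |
| 0.20 | 0.894 | 13 | 0.71 |
| 0.30 | 0.837 | 11 | 0.76 |

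These rows only convert the assumed f into other units. They are not evidence about its value.

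**The case against.** The strongest reply is that the plan does control diet. Participants are told to keep their habitual intake, that intake is characterised by a 7 day weighed diary, and each recall is compared with it. The day before each visit is therefore checked against the man's own reference. Caffeine, alcohol and vigorous exercise are restricted as well. All of this stands: a reader who inferred that only the length of the fast is fixed, or that day-before food is left wholly free, would be wrong. What remains is that the comparison with the diary comes after the event, has no stated consequence, and does not compare the two sampling days with each other.

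A second reply is that the size has no anchor. The documents name no muscle or blood analyte, so how far any of them responds to the previous day's food after a fast of at least 10 h cannot be settled from the text. This also stands, and it is why the range must start at zero.

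A third is that the reach is narrow. Sprint markers are collected at all nine sessions, and the acute session 1 samples share one previous day. The performance tests already have a standardised meal 2 h beforehand. A reader might infer that every outcome rests on one pair of visits with unmatched diet; the documents do not support that.

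Finally, repeating one day may sit awkwardly with the habitual-intake instruction if the day before session 1 was unusual, and a recalled day can be copied only approximately. Both are fair limits, though neither makes the two days less alike than they are now.

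**Conclusion.** The point holds for the baseline-to-final resting biopsy and blood deltas. They carry avoidable variation from the previous day's food, reducible but not removable, and the plan already records what is needed to reduce it.

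A reader might go further and infer bias between the arms. The documents do not support this. Allocation is randomised and participants are blinded, so variation in day-before diet costs precision between arms. A shift common to all arms cancels in the ANOVA. The within-group paired t-tests lack that protection, but nothing in the documents shows that a shift will occur, and the recall comparison might reveal one.

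The size is unknown. Under the assumption that day-before diet explains 0-30% of delta variance, matching is worth between 0% and at most 43% more participants, with the upper end requiring perfect replication. This is a cheap improvement to a partial control. It is not a flaw that undermines the trial.

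**What to change.** Add one sentence to Dietary controls. Each participant receives a copy of his session 1 24 h recall and is asked to repeat that food and drink in the 24 h before the final biopsy and blood visit. Use the recall already taken at that visit to report, by arm, how closely the two days agree in energy and macronutrients.

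The timing allows it. The final sample is taken 48-72 h after session 9, so the 24 h before it begins no sooner than 48 - 24 = 24 h after that session. The session 9 drink and post-exercise snack therefore fall outside the repeated day.

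The cost is one protocol sentence, a handout and a small burden on one day, with no extra visit or sample. Replication will be approximate.

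Doing the same for the performance tests is optional. A standardised meal already applies there. The post-intervention test falls 72-96 h after session 9, so it can follow the biopsy visit by anything from 72 - 72 = 0 h to 96 - 48 = 48 h. The day before the test may then include the fasted biopsy visit, and the pre-intervention day could not be fully repeated.
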